2.5.3 Catheter Maintenance

As suggested by the relevant literature, members of the research group designed the first draft of the MC tip positioning complication observation table. The observation table was later improved after modification by the IV specialist nurse of each hospital, and a third-party Statistics agent designed the electronic database for research. The collected data included the following two categories: ① baseline data of participants: age, sex, educational background, height, weight, diagnosis, history of thrombosis, surgical trauma, and chronic diseases, hemoglobin concentration, platelet count, white blood cell count, prothrombin time, activated partial thrombin time, history of CVC, PICC, and MC; ② Data on catheterization conditions: number of catheterizations, placement site, placement vein, and successful catheterization with the first attempt; ③ Data on the use and maintenance of catheters: daily catheter function evaluation, assessment of complications, and the time and reason of removal IV lines, and the types of antibiotics used in antimicrobial therapy.

2.6 Evaluation Indicators and Judgment Criteria

2.6.1 Incidence of Catheter-Related Complications

First, the catheter-related complications were assessed. The complications studied included phlebitis, catheter-related thrombosis, catheter occlusion, catheter dislodgement, bleeding, catheter-related infections, and infiltration. In this assessment, the incidence of each complication (i.e., number of patients with these complications) was divided by the total number of cases. Then, the total number of incidences of catheter-related complications was taken as the main outcome index (i.e., the number of patients with complications/the total number of patients). One patient with one or multiple complications was counted as one case in total.

The judgment criteria for each complication were as follows: ① phlebitis: the relevant contents in the Standard (Gorski et al., 2021) were considered; ② catheter-related thrombosis, also referred to as symptomatic thrombosis, was observed and reported either by patients or bedside nurses. Edema the limbs, neck, shoulder, chest, and/or face on the side of catheterization was observed for and reported to physicians, in order to perform an ultrasound for venous thrombosis detection; ③ catheter-related infections included local infection at the puncture site and catheter-related bloodstream infection, which were evaluated according to the corresponding diagnostic criteria in the Standard (Gorski et al., 2021); ④ catheter occlusion, inability to withdraw blood or sluggish blood return, sluggish flow; resistance or inability to flush lumen, inability to infuse fluid, Frequent occlusion alarms on electronic infusion pump. ⑤ catheter dislodgement included dislodgement of more than 3 cm; ⑥ infiltration was noted when the puncture site had liquid exudation; and ⑦ bleeding referred to the blood exudation at the puncture site 48 h after catheterization.

2.6.2 Indwelling Catheter Duration

Indwelling catheter duration referred to the number of days between the date of catheter placement and removal.

2.7 Data Collection

Catheterization nurses recorded baseline data prior to catheterization, and only the most recent results were recorded one week prior to catheterization, when multiple laboratory results were available. Catheterization site evaluations were recorded after placement, and patients were followed up for 48 h after catheterization as well as every 7th day by IV specialist nurses to review and record the progress of antimicrobial therapy. The last follow-up was conducted at the time of removal, where the reason for removal was also recorded. In addition, bedside nurses evaluated and recorded catheter functioning and complications daily.

2.8 Quality Control

Quality standards and controls were maintained throughout the study. All hospitals included in this study used the same brand and batch number of silicone-valved catheters, with a total length of 30 cm. Catheters could be trimmed to ensure a consistent length of the external catheter and a unified catheter placement and maintenance process. The same criteria were used to appoint IV specialized nurses in each hospital. Only those who had more than three years of PICC or MC

placement experience and more than 200 cases of catheterization were assigned. After catheterization, the evaluation video for catheter-related complications was sent to the nurse managers of the department in which the participants were located. Bedside nurses were trained and assessed by a nurse manager in the department. Researchers with unified training collected the relevant data, followed up, and stored the data in a dedicated electronic database. One researcher was assigned to check the data entries from each hospital, and a third-party statistics agent rechecked all entries. In case of extreme or missing values, the data were rechecked by the project coordinator of each hospital.

**Midline Catheter Tip Positioning and Catheter-Related Complications during
Antimicrobial Therapy: A Multicenter Randomized Controlled Trial**

NCT04601597

April 30, 2021

The current study followed the conformance study protocol analysis and conducted the statistical analysis using SAS 9.4 (<http://www.sas.com/>). The catheter measurement data were represented by mean and standard deviation according to the normal distribution. In contrast, the catheter measurement data with non-normal distribution were represented by median and quartile, and the number of cases or percentages represented the counting data. The catheter-measurement data between the three groups were compared through variance analysis or the Kruskal-Wallis H test. Counting data were compared using the Chi-square test, exact probability method, and Kruskal-Wallis H test. The test level $\alpha=0.05$ for all three groups was a two-sided test, and $P<0.05$ was considered a statistically significant difference. Bonferroni method was used in pairwise comparison to optimize the significance level. The test levels $\alpha=0.017$ and $P<0.017$ were statistically significant differences. To analyze the rate of complications, cumulative event rates were plotted as Kaplan-Meier curve, and differences in these rates were assessed using log-rank tests, and $P<0.0001$ was considered a statistically significant difference. Mann-Whitney U tests were performed to analyze the differences in observed event times.

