2.2 Participants

A fixed-point continuous convenience sampling method was adopted to enroll 330 participants. The participants who met the clinical criteria for this study were informed about the study and written informed consent was obtained from each participant. Consent may also have been obtained from legally authorized persons. The inclusion criteria were as follows ① estimated time of intravenous infusion ≥ 1 week before catheterization; ② age: ≥ 18 years; ③ antimicrobial therapy was only used for treatment during hospitalization, with a pH value of 5–9 and osmotic pressure < 900 mOsm/L; and ④ patients were conscious and able to communicate normally. ⑤ The catheter-to-vessel ratio is less than 45%. The exclusion criteria were as follows: ① a history of radiotherapy, thrombosis, and trauma at the catheterization site and ② plans to discharge with a catheter during the study duration. Withdrawal criteria were as follows: ① active discharge from the hospital during indwelling of the catheter; ② failure to be followed-up after catheterization due to disease; and ③ a change in health status during antimicrobial therapy treatment, requiring other drugs to be infused treatment through the MC.

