2.3 Sampling

A general formula-based sample estimation method using the data on the relationship between MC tip position and catheter-related complications was used to calculate the sample size (Wu et al., 2020). Based on the selected reference, the incidence of complications at the tip of the MC at the thoracic wall of the axillary vein was 32.5% (Wu et al., 2020), while the incidence of complications in the subclavian vein was 12.5% (Wu et al., 2020). A power analysis was performed to calculate the effect size. Efficacy was set at 0.8 (with an 80% probability of finding a difference between populations) and 0.05 (5% of Type I error). Considering external factors that may have caused loss and withdrawal, each group was increased in size by 20%, to 65 patients per group.

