2.5 Intervention

Detailed history-taking, including medical history, and clinical exams were provided to all participants were, and written informed consent was obtained. A single-blind design was adopted, in which the participants did not know their inclusion status, or whether they were in the control or experimental groups. Double blinding was avoided due to ethical concerns and the questionable efficacy of the experiment. After obtaining informed consent from the patients, the project coordinators of each hospital opened the envelopes according to their serial number. They informed the catheterization nurse about the patient's inclusion status.

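### The SAP names a single analysis set, most naturally per protocol, without defining it, and plans neither an analysis of all randomised patients nor a censoring rule for withdrawals

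*SAP*

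**What the plan says.** **Analysis set.** The SAP is one paragraph. On the population it says only: "The current study followed the conformance study protocol analysis and conducted the statistical analysis using SAS 9.4". Neither document says who belongs to that set, and neither mentions an analysis by assigned group or a sensitivity analysis.

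**Withdrawal.** Protocol 2.2 lists three grounds: "active discharge from the hospital during indwelling of the catheter"; "failure to be followed-up after catheterization due to disease"; and "a change in health status during antimicrobial therapy treatment, requiring other drugs to be infused treatment through the MC". It does not say whether such patients are analysed, replaced or dropped. Protocol 2.3 expects losses: "Considering external factors that may have caused loss and withdrawal, each group was increased in size by 20" per cent, to 65.

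**Timing of allocation.** Under Protocol 2.5, after consent, "the project coordinators of each hospital opened the envelopes according to their serial number", and the catheterisation nurse was then told the result. Allocation therefore precedes insertion.

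**Main outcome.** Protocol 2.6.1 defines it as "the number of patients with complications/the total number of patients", with each patient counted once.

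**Time to event.** The SAP adds that "cumulative event rates were plotted as Kaplan-Meier curve, and differences in these rates were assessed using log-rank tests", with significance declared at P<0.0001. Elsewhere the same paragraph sets 0.05 for the three-group test and 0.017 for pairs. Protocol 2.6.2 ends dwell time at removal and 2.7 puts the last follow-up there, but neither is stated as a censoring rule. On missing values, Protocol 2.8 provides only for rechecking entries.

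**The concern.** Each withdrawal criterion describes something that happens with the catheter in place or after catheterisation, hence after allocation. Two of the three turn on the patient's health, which may be related to complication risk. If these patients are removed, the groups compared are no longer the groups that were randomised. The contrast between tip positions can then shift if the number or the risk of those removed differs by group. Patients were blinded to group, which offers some protection, but the catheterisation nurse was not.

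The texts also point in different directions. A per-protocol label suggests that withdrawn patients leave the denominator, while a total number of patients suggests that they stay. A reader cannot tell which denominator lies behind the main result, or when a withdrawn patient, or one whose catheter came out without a complication, leaves the risk set.

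**Working it through.** **Inputs.** From the documents: 330 randomised, 110 per group (Protocol 2.4); planning risks 32.5% and 12.5% (2.3); pairwise level 0.017 (SAP). Assumed, because no withdrawal count is given: loss f of 5%, 10% or 20%; withdrawn patients at k = 1.5 to 2 times average risk; and, under no true effect, a common risk p = 22.5%, the midpoint of the planning risks.

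**The plan's own figure.** The only withdrawal-related number is 65 per group. Pooled two-proportion formula, 80% power:
- One-sided 0.05: 53, then 53 × 1.2 = 64 or 53/0.8 = 67. Both are within two patients of 65.
- Two-sided 0.05: 68, then 82 or 85. This does not reproduce 65.

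This is a separate matter. Here it shows only that loss was expected; 110 per group were randomised in any case.

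**Step 1: does the denominator matter?** Suppose 22 of 110 per arm withdraw and the remaining 88 have 29 and 11 events.
- Withdrawn excluded: 29/88 v 11/88 = 33.0% v 12.5%, difference 20.5 points.
- Kept as event-free: 29/110 v 11/110 = 26.4% v 10.0%, difference 16.4 points.
- Worst case, all 22 in the subclavian arm counted as events and none in the other: 29/110 v 33/110, difference -3.6 points.

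With 6 withdrawn per arm, the worst case is 34/110 v 19/110, p = 0.018, just above 0.017.

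**Step 2: bias from exclusion under no effect.** Retained rate = p(1 - kf)/(1 - f).

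| Scenario | Retained rates, k = 1.5 | Retained rates, k = 2 | Bias (points) | Pairwise type I error at 0.017 |
|---|---|---|---|---|
| Both arms selected, 10% v 5% loss | 21.25% v 21.91% | 20.00% v 21.32% | 0.7 to 1.3 | 1.8% to 2.0% |
| Both arms selected, 20% v 10% loss | 19.69% v 21.25% | 16.88% v 20.00% | 1.6 to 3.1 | 2.0% to 3.2% |
| One arm selected, random loss in the other, 20% each | 19.69% v 22.50% | 16.88% v 22.50% | 2.8 to 5.6 | 2.9% to 7.4% |

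Type I errors are exact for the chi-square test with 104, 99 or 88 patients left per group at 5%, 10% or 20% loss. Equal loss with equal selection gives no bias under no effect. In the one-arm scenario, withdrawn patients at half the average risk reverse the direction.

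**Step 3: a true 20-point difference, equal loss in both arms.**
- Exclusion, k = 2: 0.20(1 - 2f)/(1 - f) = 18.9, 17.8, 15.0 points at 5%, 10%, 20% loss.
- All randomised, none of the withdrawn patients' events recorded, random loss: 0.20(1 - f) = 19, 18, 16.
- The same with k = 2: 0.20(1 - 2f) = 18, 16, 12, worse than exclusion.
- Unequal loss under no effect, all randomised, none recorded: pkΔf. For 10% v 5% this is 0.225 × 1.5 × 0.05 = 1.7 to 0.225 × 2 × 0.05 = 2.3 points, also more than exclusion gives.

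So counting everyone is not sufficient when events go unrecorded, and a censored analysis is needed beside it.

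**Step 4: what censoring recovers.** Assume a 14-day course, constant hazards and k = 2. In the one-arm scenario, exclusion bias is 1.2, 2.5, 5.6 points at 5%, 10%, 20% loss. Kaplan-Meier with censoring at withdrawal leaves 0.6, 1.1, 2.4 if withdrawal is spread evenly over the course, and 1.1, 2.3, 5.1 if it falls in the first two days. Withdrawal at insertion gives the same bias as exclusion.

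**Step 5: the log-rank threshold.** For 32.5% v 12.5%, 110 per group and no loss, simulation (20,000 trials) gives pairwise power of about 90% at 0.017 and about 37% at 0.0001. Schoenfeld's formula is a cross-check: HR = ln(0.875)/ln(0.675) = 0.34; events = 110 × 0.45 = 49.5; z = 1.08 × √(49.5/4) = 3.80; power 92% and 46%.

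**The case against.** The SAP does name a basis. Read with a list of withdrawal criteria, it probably means that withdrawn patients are excluded, so calling the set simply undefined would be too strong. That stands: the set is named but not defined, and the sharper criticism is that per protocol appears to be the only analysis.

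The largest bias figures need 20% loss, twofold risk and selection in one arm only, and no passage supports one-sided selection. That stands too. Under milder unequal loss the type I error barely moves, and with equal loss and equal selection there is no bias under no effect.

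It is tempting to make the log-rank test the main comparison, since it handles partial follow-up. The documents do not support that. Protocol 2.6.1 fixes a proportion as the main outcome. The SAP is dated 30 April 2021, after the study period ended in January 2021, so changing the main test at that point would be a post hoc change. The gain also depends on an assumed course length and withdrawal timing.

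The P<0.0001 threshold is a separate issue and adds no weight to the question of the analysis set. It is raised only because the log-rank result has to be readable if it is to serve as the check.

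**Conclusion.** The point holds, as a matter that should be fixed. The plan as most naturally read removes randomised patients on partly health-related grounds after allocation. It offers no analysis of everyone randomised and gives no censoring rule. If withdrawn patients are excluded, the bias under no effect is about 0.7 to 1.3 points with 10% v 5% loss and 1.5- to twofold risk in both arms. It reaches 5.6 points only in the extreme one-arm scenario. All of this rests on assumed loss and assumed relative risk.

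A reader might infer that withdrawn patients were in fact excluded, or that the reported comparison is biased. The documents support neither: they do not say who was dropped, how many withdrew, or from which group. Nor does the SAP's date show that the set was chosen with the results in view, since nothing states when the data were examined.

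**What to change.** 1. Keep the proportion in Protocol 2.6.1 as the main outcome. Take all 330 randomised patients as denominator, in the group assigned, and count every complication recorded up to withdrawal.
2. Beside it, report the planned Kaplan-Meier and log-rank analysis of time to first complication in the same patients, censored at the withdrawal date or at uncomplicated catheter removal. State the time origin for anyone allocated but not catheterised. This is the check on counting withdrawn patients as event-free.
3. Judge the log-rank test at 0.05 for three groups and 0.017 for pairs, in line with the rest of the SAP.
4. Define per protocol, including how a tip found outside the assigned vein is classified, and keep it as a sensitivity analysis.
5. Report withdrawals by group, reason and day, with best/worst-case bounds.

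**Cost.** SAP wording and one more set of tables. Protocol 2.7 already provides for daily recording of complications, so no new visits are needed.

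**Downsides.** The all-randomised proportion can dilute a true difference, and can do worse than exclusion when withdrawn patients' events go unrecorded (step 3 of the working). Censoring may be informative, and very early withdrawal leaves most of the bias in place. Bounds have a width equal to the sum of the two groups' loss fractions: up to 10 points at 5% loss per group and 40 points at 20%.

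### Bonferroni 0.017 for the three pairwise comparisons is valid but stricter than three groups require, provided the SAP first makes pairwise testing conditional on a significant three-group test

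*SAP*

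**What the plan says.** The SAP, a single paragraph, gives two significance levels for group comparisons.

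- **Three-group comparison:** the level is 0.05; the text reads "for all three groups was a two-sided test" "and $P<0.05$ was considered a statistically significant difference".
- **Pairs:** "Bonferroni method was used in pairwise comparison to optimize the significance level", followed by "The test levels $\alpha=0.017$ and $P<0.017$ were statistically significant differences".
- **Test for proportions:** "Counting data were compared using the Chi-square test, exact probability method, and Kruskal-Wallis H test".

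No sentence says that pairs are compared only after a significant three-group result.

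Protocol 2.6.1 makes the proportion of patients with any complication the main outcome. Protocol 2.3 sizes the trial on one pair, subclavian (12.5%) versus axillary vein at the chest wall (32.5%), with 80% power and a type I error of 0.05 that is not divided by three; "each group was increased in size by 20%, to 65 patients per group". Protocol 2.4 reports 110 randomized per group.

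**The concern.** The trial asks which tip position differs from which, and only the pairwise tests answer that. A three-group P value does not. The SAP has a three-group test at 0.05 and also divides 0.05 by three for the pairs. With exactly three groups, the three-group test can supply the protection that the division is meant to give. If it is used that way, the stricter pairwise level costs power and is not needed to hold the family-wise error at 0.05. At stake is the chance of separating two positions, above all in comparisons with the control group, where differences may be modest.

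**Working it through.** **Inputs.** Levels 0.05 and 0.017, two-sided, chi-square test (SAP). Rates 12.5% and 32.5% (Protocol 2.3). 110 per group (Protocol 2.4), or 88 if the 20% loss allowance of 2.3 is applied (110 × 0.8). The documents give no control rate, so it is an assumption and is varied.

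**The plan's own figures.** 0.05/3 = 0.0167, rounded to 0.017. The 65 per group in 2.3 is reproduced to within two patients by a one-sided 0.05: 53 per group, then 53 × 1.2 = 64 or 53/0.8 = 67. A two-sided 0.05 gives 68, then 82 or 85. That is a separate matter and is not pursued here.

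**Why three groups are special.** Call the pairwise nulls p1 = p2, p1 = p3 and p2 = p3. If any two are true, all three rates are equal, so every intersection of pairwise nulls is the global null. A closed test therefore needs only the global test at 0.05 and each pair at 0.05. If all rates are equal, a false pairwise claim requires a false global rejection (probability about 0.05). If exactly one pair is equal, only one true null can be rejected, and it is tested at 0.05. Exactly two true pairwise nulls cannot occur.

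**Family-wise error by simulation** (Pearson chi-square, 54 to 110 per group):

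| Procedure | All rates equal | One pair equal |
|---|---|---|
| Pairs at 0.05 after a significant three-group test | 0.049–0.051 | 0.047–0.052 |
| Pairs at 0.05, no condition | 0.117–0.126 | not run |
| Pairs at 0.017, no condition | 0.040–0.047 | 0.016–0.018 |

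A further set of runs gave 0.056 for the closed test in one setting (88 per group; rates 12.5%, 45%, 45%). The pairwise chi-square alone is equally liberal there, so this comes from the chi-square approximation and not from the closed-test argument.

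**Power, documented pair, 110 per group.** Power = Φ{[|p1 − p2| − z√(2p̄(1 − p̄)/n)] / √([p1(1 − p1) + p2(1 − p2)]/n)}, with p̄ = 0.225.

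- √(2 × 0.225 × 0.775/110) = 0.0563
- √((0.2194 + 0.1094)/110) = 0.0547
- At 0.05: (0.200 − 1.960 × 0.0563)/0.0547 = 1.64, power 0.949
- At 0.017: (0.200 − 2.387 × 0.0563)/0.0547 = 1.20, power 0.885

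This 6.5-point gap ignores the three-group condition. Simulation with the condition counted gives:

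| Assumed control rate | 0.017 | Closed test |
|---|---|---|
| 12.5% | 0.895 | 0.946 |
| 22.5% | 0.894 | 0.907 |
| 32.5% | 0.895 | 0.941 |
| 40% | 0.895 | 0.952 |
| 50% | 0.894 | 0.953 |

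The gain is 1 to 6 points. At 88 per group, power goes from 0.805 to 0.828–0.903.

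**Power, pairs with control, 110 per group** (control rate assumed):

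| Pair | Control rate | 0.017 | Holm | Closed test |
|---|---|---|---|---|
| Chest wall vs control | 45% | 0.314 | 0.470 | 0.477 |
| Chest wall vs control | 20% | 0.392 | 0.47 | 0.555 |
| Subclavian vs control | 22.5% | 0.335 | 0.411 | 0.494 |

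For the documented pair, Holm gives 0.90–0.94.

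**The case against.** **Bonferroni is a legitimate choice.** It is standard, valid and stated with an explicit threshold, and it needs no preceding test. Choosing among valid multiplicity methods is partly a matter of discretion. This stands, and it is why the point is not a defect.

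**A reader might infer that 0.017 is already redundant.** The SAP does not support that. It lists two thresholds and does not link them, so as written 0.017 is the only stated protection for pairwise claims. Removing it without adding the condition would raise the family-wise error to about 0.12.

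**A reader might infer that the plan costs the trial about 16 points of power.** The documents do not support that either. Such gains arise only for pairs with control, at control rates that have to be assumed, and power in those cases stays at about 0.48 to 0.56 even after the change. For the pair on which the trial was sized, 0.017 already gives about 0.89 at 110 per group, above the planned 80%. In the settings checked, the chance of declaring at least one pairwise difference changes by about one point or less.

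**The mismatch with Protocol 2.3** (sized at 0.05, tested at 0.017) does not show that Bonferroni is wrong. At two-sided 0.017, 80% power needs 90 per group, or 90 × 1.2 = 108 or 90/0.8 = 113 with the allowance. The 110 randomized largely absorbs this.

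**Timing.** The SAP is dated April 30, 2021, and Protocol 2.1 ends the study period in January 2021. Relaxing a stated threshold after that could look data-driven. This stands and limits how the fix may be used.

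**The closed test is not better in every single data set.** A pair can reach P<0.017 while the three-group test misses 0.05. At 110 per group with control at 22.5%, requiring the three-group test lowers power at 0.017 from 0.894 to 0.890. The net gain was still positive in every setting run.

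**Conclusion.** The point holds as an optional efficiency improvement. The pairwise level of 0.017 is valid, and it is stricter than three groups need only once pairwise testing is made explicitly conditional on the three-group test. The gain at 110 per group is 1 to 6 points for the pair with documented rates, and at most about 16 points for pairs with control at assumed control rates of 20% to 45%. These figures assume independent binary outcomes, chi-square tests, the rates in Protocol 2.3, and 110 evaluable patients per group. The argument applies to the proportion outcome of Protocol 2.6.1. It does not carry over to the log-rank analysis, for which the SAP states a separate P<0.0001 criterion.

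**What to change.** For the proportion outcome, replace the Bonferroni sentence and its 0.017 threshold with: *Pairwise comparisons are made only if the three-group test is significant at two-sided 0.05; each pair is then tested at two-sided 0.05 (closed test for three groups).* Report pairwise risk differences with 95% intervals.

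If a method without the condition is preferred, use Holm. It never rejects less than Bonferroni and recovers part of the gain.

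The cost is one SAP sentence and two caveats. Ordinary 95% pairwise intervals are not simultaneous intervals. The change should be made only if pairwise results are not yet known; otherwise keep 0.017 as the stated analysis and report the closed test or Holm beside it as a sensitivity analysis. Any pairwise log-rank comparison would need its own three-group log-rank test as the condition.

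### The Kaplan-Meier plot of cumulative complication rates probably censors complication-free catheter removal, so its later part would read above the actual share of patients with a complication

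*SAP*

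**What the plan says.** The SAP, a single paragraph, analyses complications over time as follows: "cumulative event rates were plotted as Kaplan-Meier curve", and "differences in these rates were assessed using log-rank tests". It states no censoring rule and names no competing-risk method.

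Protocol section 2.6.1 defines the main outcome as a plain proportion, "the number of patients with complications/the total number of patients", and adds that "One patient with one or multiple complications was counted as one case in total".

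On follow-up, section 2.7 states: "The last follow-up was conducted at the time of removal, where the reason for removal was also recorded". Section 2.6.2 makes dwell time an outcome in its own right: "Indwelling catheter duration referred to the number of days between the date of catheter placement and removal". Section 2.2 sets a lower bound on expected therapy, "estimated time of intravenous infusion ≥ 1 week before catheterization", and no upper bound. It also excludes patients who expect to go home with the catheter in place.

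**The concern.** A patient whose catheter is taken out without a complication can no longer have a catheter occlusion, dislodgement or infiltration. If that patient is censored, Kaplan-Meier treats them as still able to have one, at the same rate as those whose catheter remains in. One minus Kaplan-Meier then estimates the risk in a setting where no catheter is ever removed complication-free. That is not the proportion in section 2.6.1, yet the SAP calls the plotted quantity a cumulative event rate.

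What is at stake is how the plot is read. Absolute risks taken from its later part, and absolute differences between tip positions, would be larger than the trial's own main outcome shows.

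**Working it through.** **No planned figure to reproduce.** The documents give no expected curve, dwell distribution or landmark risk. The direction of the gap follows from algebra; its size needs assumptions.

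**Direction.** At a time when d of n patients at risk have a first complication:

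- one minus Kaplan-Meier rises by KM × d/n, where KM is reduced only by earlier complications;
- the cumulative incidence (Aalen-Johansen) rises by S × d/n, where S is reduced by earlier complications and by earlier complication-free removals.

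S never exceeds KM, so one minus Kaplan-Meier is never below the cumulative incidence. It is above it as soon as one complication follows another patient's complication-free removal. If everyone is followed to complication or removal, the cumulative incidence ends exactly at the crude proportion.

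**Inputs for size.**

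- True proportions of 32.5% and 12.5%: the planning rates in protocol section 2.3.
- Group size 110: section 2.4.
- Planned dwell X (assumed): 7 days plus a log-normal part with median 7 days and log-scale SD s of 0.4 or 0.6. The 7-day minimum respects the entry criterion.
- Constant complication hazard h per day (assumed).

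**Formulas.**

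- h solves p = E[1 − exp(−hX)].
- One minus Kaplan-Meier at day t: 1 − exp(−ht).
- Cumulative incidence at day t: E[1 − exp(−h·min(X, t))].
- Expected number at risk at percentile q of planned dwell: 110 × (1 − q) × exp(−ht).

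Example, p = 32.5% and s = 0.4: h = 0.0272. The 90th percentile of X is 7 + 7·exp(0.4 × 1.2816) = 18.7 days. One minus Kaplan-Meier is 1 − exp(−0.0272 × 18.7), about 40%. The cumulative incidence is 32.1%. The expected number at risk is 110 × 0.1 × 0.60, about 6.6.

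| True p | s | h | Percentile of X (day) | 1 − KM | Cumulative incidence | At risk of 110 |
|---|---|---|---|---|---|---|
| 32.5% | 0.4 | 0.0272 | 50th (14.0) | 31.7% | 30.0% | 38 |
| 32.5% | 0.4 | 0.0272 | 90th (18.7) | 39.8% | 32.1% | 7 |
| 32.5% | 0.6 | 0.0262 | 50th (14.0) | 30.7% | 28.4% | 38 |
| 32.5% | 0.6 | 0.0262 | 90th (22.1) | 43.9% | 31.8% | 6 |
| 12.5% | 0.4 | 0.0092 | 50th (14.0) | 12.1% | 11.3% | 48 |
| 12.5% | 0.4 | 0.0092 | 90th (18.7) | 15.8% | 12.3% | 9 |
| 12.5% | 0.6 | 0.0088 | 50th (14.0) | 11.5% | 10.6% | 49 |
| 12.5% | 0.6 | 0.0088 | 90th (22.1) | 17.6% | 12.1% | 9 |

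At the 90th percentile the difference between the two groups reads 39.8 − 15.8 = 24.0 points (s = 0.4) or 43.9 − 17.6 = 26.3 points (s = 0.6). The cumulative incidences differ by 32.1 − 12.3 = 19.8 and 31.8 − 12.1 = 19.7 points.

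**Sensitivity** (300 simulated arms of 110, crude proportion 32.5%):

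- All dwell times fixed at 14 days: no gap.
- Dwell about normal, mean 14 and SD 2 days, constant hazard: 31.5% against 30.4% at day 14.
- Dwell 7 days plus an exponential part with mean 7 days: 45.0% against 31.5% at day 21 with a constant hazard, and 39.8% against 31.7% with a falling hazard (Weibull shape 0.6).

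In one constructed arm with every complication before the first complication-free removal, both estimates were 32.7%.

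**The case against.** **The censoring is inferred.** The SAP does not say how removal is handled. If complication-free patients were carried forward as event-free to a common horizon, one minus Kaplan-Meier would equal the crude proportion and there would be no gap. This stands as a limit on certainty. However, neither document describes that convention, and the protocol ends follow-up at removal, so censoring is the likelier reading.

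**The gap is small where most of the data are.** This also stands. At the median planned dwell it is about 1 to 2 points in the illustration. At the 90th percentile only about 6 to 9 of 110 patients remain at risk, and still later values rest on almost nobody. They should not be used to show the size of the problem.

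**Kaplan-Meier describes a legitimate quantity.** It can be read as complication risk while a catheter stays in place, and it matches the log-rank test. That would justify a plot labelled in those terms. It does not justify calling the plotted values cumulative event rates when the main outcome is a proportion of all patients.

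**A reader might infer that the trial's main comparison is biased.** The documents do not support this. The main outcome is a crude proportion, and the SAP compares counts by chi-square or exact methods. The log-rank test remains a valid comparison of complication hazards while the catheter is in place. No risk or risk difference read from the curve is planned.

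**A reader might also infer that most catheters leave follow-up because therapy ended.** The protocol says only that the reason for removal is recorded, not how often each reason occurs.

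**Conclusion.** The point holds for the plotted absolute rates only. If complication-free removal is censored and dwell times vary, the curve lies above the actual proportion of patients with a complication, mainly in its later part. Varying dwell is very likely, because expected therapy has a lower bound of one week and no upper bound, and dwell time is itself an outcome.

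Under the assumed dwell distributions and a constant hazard, the excess at the 90th percentile of planned dwell is about 8 to 12 points in a 32.5% group and about 3 to 6 points in a 12.5% group. The true size is unknown because the documents give no dwell distribution, and it is zero if all dwell times are equal. A falling hazard makes it smaller.

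The exact match between the cumulative incidence and the crude proportion assumes that everyone is followed to complication or removal. If withdrawn patients are kept and censored, the two may differ slightly.

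**What to change.** In the SAP, replace the Kaplan-Meier plot with the Aalen-Johansen cumulative incidence of first complication by group, with removal without a prior complication as the competing event. State how withdrawn patients are handled, and show the numbers at risk under the plot. Keep the log-rank test and label it as a comparison of complication hazards while the catheter is in place.

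The cost is a few SAP sentences and a standard software option. The time and reason of removal are already collected (protocol sections 2.5.3 and 2.7). The small downside is that the curve then shows actual risk while the test compares hazards, which needs one line of explanation in the report.
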